#### **4.8.2.2 Deaths**

The following deaths summaries will be generated on the safety analysis set.

- Number (%) of patients who died during the study and reasons for death
- Number (%) of patients who died within 30 days after last dose of study drug except deaths occurred after taking any subsequent anticancer therapy/procedure and reasons for death

All deaths will be listed.

#### **4.8.3 Laboratory Data**

Laboratory data of hematology, biochemistry, coagulation, and urinalysis up to the end of study visit will be reported in SI units.

Descriptive statistics (mean, standard deviation, median, and range) will be calculated for the raw data and for their changes from baseline at each scheduled assessment for hematology, biochemistry, coagulation. All results will be summarized using shift from baseline. Shifts for clinical laboratory results that can be graded according to CTCAE version 4.0 will be summarized by CTCAE grade.

Summaries by visit will include data from scheduled assessments, and all data will be reported according to the nominal visit date for which it was recorded. Unscheduled data will be included in “worst case post-baseline” summaries, which will capture a worst case across all scheduled and unscheduled visits after the first dose of study treatment.

Summary analyses will include data up to the start of subsequent anticancer therapy/procedure.

All laboratory data, including urinalysis, will be listed. Pregnancy test results will not be listed, but will be included in datasets.

#### **4.8.4 Electrocardiogram**

Electrocardiogram (ECG) parameters (e.g., corrected QT interval [QTc] in ms) will not be converted or derived, but will be reported as provided by investigational sites.

Descriptive statistics (mean, standard deviation, median, and range) will be calculated for the raw data and for their changes from baseline at each scheduled assessment.

The following abnormal QTc (including QTcF, QTcB and QTc with unspecified method) will be reported:

At any post-baseline with absolute value

>450 - <=480 ms

>480 - <=500 ms

> 500 ms

Change from Baseline

>30 – <=60 ms

>60 ms

For patients with unspecified QTc method at either baseline or post-baseline, consistent correction method is assumed within a patient when calculating the change from baseline.

Summary analyses will include data up to the start of subsequent anticancer therapy/procedure.

All ECG data will be listed, both for quantitative data and for overall impression.

#### **4.8.5 Vital Signs**

Descriptive statistics (mean, standard deviation, median, and range) for vital signs data, including systolic and diastolic blood pressure, heart rate, respiration rate, and body temperature will be calculated for the raw data and for their changes from baseline at each scheduled assessment.

Summary analyses will include data up to the start of subsequent anticancer therapy/procedure.

All vital signs data will be listed together with body weight and ECOG performance score.

#### **4.8.6 ECOG Performance Status**

ECOG performance score data will be listed together with vital signs and body weight.

#### **4.8.7 Physical Examinations and Body Weight**

Physical examination will be performed according to protocol. Clinically significant findings from the physical examinations will be recorded as medical history (prior to first administration of ADCT-301) or AEs (subsequent to first administration of ADCT-301).

Body weight will be listed together with vital signs and ECOG performance score.

#### **4.9 Efficacy Analyses**

Disease assessment will be performed according to protocol. The endpoints described in this section use the investigator's evaluation according to the Lugano Classification criteria or Global Response Score Grading Scales for CTCL patients and clinical progression from End of Treatment (EOT)/Study disposition page.

Tumor assessment data (target lesions, non-target lesions, and new lesions, overall response, SUV max, Deauville score, etc.) for non-CTCL patients, and modified Severity-Weighted Assessment Tool (mSWAT) scores for CTCL patients will be listed. A separate listing will contain derived data for DOR, PFS, and OS.

#### **4.9.1 Overall Response Rate**

Overall response rate is defined as the proportion of patients who achieve either CR or PR as best overall response as assessed by investigators according to the Lugano Classification criteria or Global Response Score Grading Scales for CTCL patients before the start of subsequent anticancer therapy or procedure.

The order of overall response category is: CR, PR, SD, NE, PD (including disease recurrence/relapse). The overall response category will be derived based on response assessment performed on or before the start of subsequent anticancer therapy/procedure. Patients without documented subsequent anticancer therapy and/or with missing start date of anticancer therapy will be considered as not having received subsequent anticancer therapy. If a patient only has one valid disease assessment which is SD, and the assessment is within 35 days after the first dose, the overall response for this patient will be considered as NE.

The overall response rate and the corresponding 95% two-sided exact confidence interval at each dose level will be presented. Subgroup analysis may be provided if relevant.

Percent change from baseline in the sum of product of diameters (SPD) for target lesions for non-CTCL patients and mSWAT total score for CICL patients will be presented for available data in the efficacy analysis set by dose level. These data will also be displayed as a waterfall plot, with vertical bars representing the sorted values of best percent reduction for each patient.

Tumor response and lesion measurement (or mSWAT) will be listed by assessment visit.

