8.2.2 Secondary Endpoints

The following secondary endpoints will be determined in Part 1 and Part 2:

- Evaluate response to ADCT-301 using the Lugano Classification Criteria (2014) ([Appendix 13.2](#)) and Global Response Score Grading Scales for CTCL ([Appendix 13.3](#)) through the evaluation of complete response (CR), partial response (PR), progressive disease (PD), and stable disease (SD).
- Characterize PK profile of HuMax-TAC (total antibody; drug-to-antibody ratio [DAR] ≥ 0), PBD-conjugated HuMax-TAC (DAR ≥ 1), and free warhead SG3199 (see [Section 8.6.3](#)).
- Determine anti-drug antibodies ADAs in blood before, during, and after treatment with ADCT-301.

[REDACTED]

[REDACTED]

[REDACTED]

[REDACTED]

[REDACTED]

[REDACTED]

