### **4.9.4 Progression-free Survival**

Progression-free survival is defined as the interval between the date of first dose and the date of disease progression (based on radiographic or clinical progression at EOT/EOS) or death, whichever occurs first. Patients who have the event after the start of subsequent anticancer therapy/procedure, or who are progression-free and alive at the time of clinical cutoff, or have unknown status, will be censored at the time of their last valid disease assessment on or before the start of subsequent anticancer therapy/procedure or clinical cut-off.

Patients with no post-baseline disease assessment will be censored on Day 1.

PFS will be estimated and displayed by dose levels for the efficacy analysis set using Kaplan-Meier methods (SAS® PROC LIFETEST). Patients who do not have a PFS event during or after the study will be censored. A Kaplan-Meier plot will be presented.

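### SAP 4.9.1 ranks NE above PD, so a patient whose only assessments before documented progression are not evaluable is tabulated as NE and the PD count is understated

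*SAP*

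**What the plan says.** SAP 4.9.1 begins with the endpoint: "Overall response rate is defined as the proportion of patients who achieve either CR or PR as best overall response as assessed by investigators". It then gives the ranking from which the category is taken: "The order of overall response category is: CR, PR, SD, NE, PD (including disease recurrence/relapse". The assessments that count are limited by date: "The overall response category will be derived based on response assessment performed on or before the start of subsequent anticancer therapy/procedure".

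One exception deals with early stable disease. It opens "If a patient only has one valid disease assessment which is SD, and the assessment is within 35 days after the first dose", and in that case the patient is set to NE. It covers no other pattern.

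On reporting, the same section says "The overall response rate and the corresponding 95% two-sided exact confidence interval at each dose level will be presented". It also plans by-visit listings of tumor response.

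Protocol 8.2.2 describes the response secondary endpoint as assessed "through the evaluation of complete response (CR), partial response (PR), progressive disease (PD), and stable disease (SD". PD is therefore a category the study set out to evaluate, not just what is left after responders are counted.

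PFS is derived separately, in SAP 4.9.4: "Progression-free survival is defined as the interval between the date of first dose and the date of disease progression". It works from dates and does not use the category ranking.

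**The concern.** A best-response ranking should let an informative result take precedence over an uninformative one. NE says that an assessment could not be classified; PD says that the disease was seen to progress. With NE ranked higher, an unreadable scan overrides a later, documented outcome. The SAP does not treat NE this way elsewhere: in the subgroup list of 4.9.2, response to prior therapy groups NE with missing data, while PD counts as refractory disease.

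The early-SD exception has a similar flaw. It implies that one SD within 35 days is too little evidence of stability. A PD at the next assessment does not add evidence of stability, yet it is what lets the SD stand.

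At stake is the accuracy of the PD, NE and SD counts in a best-response breakdown by dose level, where groups are small and one patient is visible.

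**Working it through.** No figure in the documents depends on the ranking, so there is nothing to reproduce. The check applies the rule to possible assessment histories.

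**Inputs.** Ranking and 35-day exception: SAP 4.9.1. Scan timing: Protocol 5.1.2 and 7.1. Cohort size of about 10 and Part 2 size of about 60: Protocol 8.3. The ranking is read as best to worst, and best response as the highest-ranked category among a patient's assessments.

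**Step 1: which histories change if PD is ranked above NE.** Take all sequences of one to three assessments over CR, PR, SD, NE and PD, ending at the first PD. There are 5 of length one, 4 × 5 = 20 of length two and 4 × 4 × 5 = 80 of length three: 5 + 20 + 80 = 105.

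| Assessments | Sequences | Category changes | Which | Responder status changes |
|---|---|---|---|---|
| 1 | 5 | 0 | none | 0 |
| 2 | 20 | 1 | NE, PD: NE becomes PD | 0 |
| 3 | 80 | 1 | NE, NE, PD: NE becomes PD | 0 |

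These count patterns; they are not patient probabilities. They show that the error is confined to NE-only histories ending in PD, and that it runs one way. A single PD assessment stays PD under either ranking.

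**Step 2: the early-SD exception.** Compare two patients with SD on day 33:
- no further assessment: the exception applies, so the category is NE;
- PD at the next assessment: there are two assessments, the exception does not apply, and SD outranks PD, so the category is SD.

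The patient with documented progression gets the better category.

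**Step 3: can a first scan fall within 35 days?**
- Protocol 7.1: 6 weeks ± 1 week is 42 − 7 = 35 to 42 + 7 = 49 days, so only the earliest permitted day qualifies.
- Protocol 5.1.2: up to 6 days before Cycle 3 Day 1, itself movable by 3 days, gives 42 − 3 − 6 = day 33.
- If the 3-day window were used in both preceding cycles (two 18-day cycles), the figure would be 36 − 6 = day 30.

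On the planned calendar, then, an in-window first scan can fall at about day 33 to 35. Both sections also allow extra scans when clinically needed, and these can be earlier.

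**Step 4: size.** One reclassified patient is 1/10 = 10 percentage points in a cohort of about 10, and 1/60 = 1.7 points across Part 2. The documents give no rate for NE followed by PD. If, purely as an assumption, it were 2% to 10% of patients, the shift would be 0.2 to 1 of 10, 1.2 to 6 of 60, or 2.8 to 14 of all 140.

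**The case against.** The strongest reply is that almost nothing reported depends on this. SAP 4.9.1 commits to the response rate with an exact interval, percent change in lesion size or skin score, and a waterfall plot; none uses the order of NE and PD. No hypothesis is tested, the primary objectives concern safety and dose, and by-visit listings still show the PD. All of this stands, and it is why the point is minor. It does not make the category right, and Protocol 8.2.2 names PD among the categories to be evaluated.

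It may also be said that NE is meant only for patients with nothing else on record, so it never competes with PD. In that case it would need no place above PD, and the SAP does not state that limit.

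On early SD, the protocol's SD definitions set no minimum duration, so the 35-day condition is the SAP's own convention. That is fair. But the convention gives an inconsistent result on its own terms.

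A reader might infer several stronger things that the documents do not support:
- That patients who progress are generally reported as NE or stable. Patients with PD only stay PD.
- That ranking SD above PD is itself an error. Putting SD ahead of a later PD is the ordinary meaning of best response; only the early-SD case is open to question.
- That a non-PD best response alongside a PFS event exposes a fault. The two endpoints measure different things, and any patient who responds or is stable and later progresses shows the same difference.
- That a rate of SD or better is distorted. The SAP defines none. The order of NE and PD could not alter one, since neither would count; only the early-SD case could.

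**Conclusion.** Wrong as written; minor severity. The ranking in SAP 4.9.1 classes NE-only histories ending in documented PD as NE, which understates PD in the best-response breakdown. As an edge case, an SD within 35 days followed by PD remains SD, although the same SD with nothing after it becomes NE.

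The response rate and its interval, duration of response, PFS and OS are unaffected. The size is one count per affected patient, as worked above; how many patients are affected cannot be derived from the documents. The conclusion assumes that the list runs from best to worst and that an NE assessment enters the ranking alongside the others.

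**What to change.** In SAP 4.9.1:
- change the order to CR, PR, SD, PD, NE, with relapse still counted under PD;
- state that NE is assigned only when no assessment supports CR, PR, SD or PD, keeping the existing rule that a sole SD within 35 days does not support SD;
- state that an SD within 35 days followed by PD, with no later SD or better, is classed as PD.

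While the paragraph is open, it would help to say whether clinical progression counts as PD for best response. SAP 4.9 lists "clinical progression from End of Treatment (EOT)/Study disposition page" as an input to the efficacy endpoints, but 4.9.1 does not say how it enters. That is a clarification, separate from the error above.

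The cost is one or two SAP sentences and the matching derivation code. No new data are needed.

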8.6 Statistical Analysis Methodology

8.6.1 Efficacy Analysis

8.6.1.1 Overall Response Rate

Overall response rate is defined as the proportion of patients with best overall response of PR or CR at the time each patient discontinues treatment with ADCT-301 ([Appendix 13.2](#), [Appendix 13.3](#)).

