## 6 Data handling conventions

### 6.1 General conventions

#### 6.1.1 Missing data

##### Handling of missing/partial dates

In general, imputation of missing dates will be made for AE onset date, AE resolution date, date of death, medication start/end dates, start and end dates of prior and subsequent therapies, and date of initial diagnosis for reporting. No imputation should be done at the data level.

- If dates are completely missing, no imputation will be made.
- For any partial date with missing year, no imputation will be made.
- For missing initial diagnosis date, if only day is missing, then the 1st of the month will be used; if only year is present, then Jan 1st will be used. If such imputed date for initial diagnosis is on or after date of first dose, then date of first dose - 1 will be used.
- If the imputed date is for an AE start date and is in the same year and month as but before the first dose date, then the first dose date will be used, or if the imputed AE start date is after the AE end date, then the AE end date will be used. If the imputed date is for an AE start date and is in the same year and month as but after the last dose date + 84 days, then the last dose date + 84 days will be used.
- If a medication date or time is missing or partially missing, so it cannot be determined whether it was taken prior or concomitantly, it will be considered as a prior and concomitant medication.
- If the imputed date is for a date of death and is before the last date that the patient is known to be alive, the latter date will be used.
- If the date part is missing for new anticancer therapy, the month and year will be used for comparison with disease assessment.

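### A recorded subsequent therapy with no usable start date removes the ORR cut-off, so a response to another treatment can be counted for ADCT-301

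*SAP*

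**What the plan says.** SAP 4.9.1 sets a clear cut-off for ORR: "The overall response category will be derived based on response assessment performed on or before the start of subsequent anticancer therapy/procedure". Shortly afterwards it says that patients "with missing start date of anticancer therapy will be considered as not having received subsequent anticancer therapy". Best response is then taken from a ranking: "The order of overall response category is: CR, PR, SD, NE, PD". No stop at first progression is stated.

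SAP 6.1.1 covers incomplete dates in three relevant lines:
- "If dates are completely missing, no imputation will be made"
- "For any partial date with missing year, no imputation will be made"
- "If the date part is missing for new anticancer therapy, the month and year will be used for comparison with disease assessment"

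Protocol 8.6.1.1 defines ORR differently, by "best overall response of PR or CR at the time each patient discontinues treatment with ADCT-301". SAP 4.9.1 does not carry that limit over. SAP 3.3, which lists changes to the protocol's statistical section, mentions only the efficacy analysis set.

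DOR and PFS (SAP 4.9.2 and 4.9.4) also depend on the start of new therapy. Under PFS, patients with an event after that start are "censored at the time of their last valid disease assessment on or before the start of subsequent anticancer therapy/procedure". The sentence about missing start dates appears only under ORR.

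**The concern.** When the database shows that a patient went on to another treatment, a missing date does not make that fact doubtful. It only makes its timing unknown. The SAP resolves the unknown timing by setting the fact aside. Every later assessment then qualifies for best response, and because the ranking takes the best category, a CR or PR obtained on the other treatment becomes the patient's response to ADCT-301.

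The SAP treats missing safety information the other way. An incomplete AE onset date defaults to treatment-emergent (4.8.2.1), and a missing causality assessment defaults to related (6.1.1). Missing efficacy information here defaults in favour of the drug.

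ORR is a secondary, descriptive endpoint and SAP section 4 rules out hypothesis testing, so no error rate is at stake. What is at stake is the response count at a dose level or in a small expansion cohort, where one patient carries much weight.

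**Working it through.** The plan gives no ORR, power or precision figure tied to this rule, so there is nothing to reproduce. The check is to trace the rule, then scale it.

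**1. Which dates are affected.** SAP 6.1.1 imputes nothing if the date is wholly missing or lacks the year. If month and year are known, they are compared with the assessment date. The gap is therefore confined to recorded therapies without a usable month and year.

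**2. What happens to ORR.** With no start date, the cut-off cannot be applied, and SAP 4.9.1 directs that the patient be handled as having had no new therapy. All assessments then count. Adding assessments to a best-of ranking can raise a patient's category but not lower it, so responders can be gained and not lost.

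**3. Whether a later assessment would exist.** Protocol 5.1.6 ends scheduled scans at progression or at new therapy. It makes a separate provision for patients who stop for a stem cell transplant: their imaging follows the transplant centre's schedule. SAP 4.7.3 counts transplant as a subsequent therapy or procedure. An undated transplant followed by a CR scan is thus a concrete route; an off-schedule scan is another.

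**4. What happens to DOR and PFS if the same convention is used.** Suppose new therapy starts at month 3 and the patient dies at month 5.
- Start date known: the death falls after new therapy, so the patient is censored at the last valid assessment up to month 3.
- Start date missing: the patient counts as untreated, and the death is an event at month 5.

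A patient who stays progression-free on the other therapy is instead followed for longer without an event. The first effect adds events and the second adds event-free time. The documents do not say which would dominate.

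**5. Scale for ORR.** The responder counts are assumed. Cohorts of about 10 come from Protocol 8.3; 60 (Part 2) and 140 (total) come from Protocol 8.3 and SAP 3.1. The exact 95% limits are the 2.5% quantile of Beta(x, n−x+1) and the 97.5% quantile of Beta(x+1, n−x).

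| n | Without the misattributed response | With it | Change (1/n) |
|---|---|---|---|
| 10 | 3/10 = 30.0% (6.7 to 65.2) | 4/10 = 40.0% (12.2 to 73.8) | 10 points |
| 60 | 18/60 = 30.0% (18.8 to 43.2) | 19/60 = 31.7% (20.3 to 45.0) | 1.7 points |
| 140 | 42/140 = 30.0% (22.6 to 38.3) | 43/140 = 30.7% (23.2 to 39.1) | 0.7 points |

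**6. Expected inflation.** Let f be the share of patients who did not respond to ADCT-301 and have an undated new therapy with a later scan. Let r be their response rate on that therapy. Inflation is f × r. Both ranges are assumptions:
- Low: 0.01 × 0.20 = 0.2 points, or 60 × 0.002 = 0.12 patients of 60.
- High: 0.05 × 0.60 = 3.0 points, or 60 × 0.03 = 1.8 patients of 60.

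**The case against.** The strongest reply is that the route is narrow. A false responder needs four things together: a recorded therapy, no usable start date, a later response assessment in the database, and no earlier response to ADCT-301. Scheduled scans stop at new therapy, and Protocol 5.1.5 places the End of Treatment assessments before it. The start date is a collected item, and both the subsequent therapies and the responses by visit are listed (SAP 4.7.3 and 4.9.1), so an alert reader could find such a patient. The intervals above also overlap almost entirely.

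All of this stands, and it keeps the point minor. It does not remove it: a listing does not change the derived ORR, transplant imaging remains open, and no count of affected patients or sensitivity analysis is planned.

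A reader might also infer that the rule favours the drug in DOR and PFS. The documents do not support that. SAP 4.9.2 and 4.9.4 censor events after new therapy, so losing the start date turns a later progression or death into a counted event. Deaths are still sought after new therapy, through the telephone contacts in Protocol 5.1.6. The one-directional argument holds for ORR only.

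A second objection concerns the remedy. Dating the unknown start to the day after the last dose would be too harsh. Protocol 5.1.2 puts scans within 6 days before Day 1 of Cycles 3, 5, 8 and so on. On a 21-day cycle that is 15 to 21 days after the preceding dose (21 − 6 = 15). Genuine responses to ADCT-301 would be discarded, so a later cut-off is needed.

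**Conclusion.** The point holds as a minor gap in the ORR definition. For recorded therapy without a usable month and year, SAP 4.9.1 removes its own cut-off, SAP 6.1.1 does not restore it, and the protocol limit that would largely have done so was not carried over. Any resulting ORR error is upward.

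Its size depends on a frequency that the documents do not give. One misattributed response is worth 10 points in a cohort of 10 and 1.7 points in 60 patients. Under the assumed ranges for f and r, the expected inflation is 0.2 to 3.0 points.

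For DOR and PFS, the conclusion is only that censoring at new therapy would fail for these patients if the convention is applied there. The net direction is undetermined. No test or error rate is affected.

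**What to change.** Replace the missing-date clause in SAP 4.9.1 with a rule of this kind: where subsequent therapy is recorded but its start has no usable month and year, only disease assessments up to and including the End of Treatment visit count for ORR, or up to a later documented contact confirming that no new therapy had begun. The visit is a sound anchor because Protocol 5.1.5 schedules it before any new anticancer treatment. It also keeps scans made after the last dose.

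Use the same date as the censoring cut-off in SAP 4.9.2 and 4.9.4, so that all three endpoints share one convention. Query the missing dates, report the number of patients affected, and show ORR, DOR and PFS under the rule as now written as a sensitivity analysis.

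The cost is one SAP sentence with cross-references and no new data collection. ORR may come out slightly lower, and a few genuine late responses first seen after the End of Treatment visit may be excluded. In DOR and PFS, some later events would become censored observations.
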